7.22 Insulin

Patients will use their own rapid-acting analogue insulin (novolog, humalog) during this study.

7.23 Supplies

Study pump, study meters and sensors are supplied with additional, commercially available materials i.e., reservoirs, infusion sets, alcohol wipes, meter supplies, tape, etc. free of charge.

7.24 Packaging

In Europe, all devices will be labeled in accordance with local language requirements.

Labeling for the study devices will be provided under separate cover. Investigational devices will be labeled in accordance to their regulatory requirements.

7.25 Product Training Requirements

Training of the investigational center staff on the conduct of the study and system being studied will be initiated before the protocol is implemented. All participating physicians and coordinators will be familiarized with the system. Specific investigational center staff will be trained on each of the system's components. Training will contain both lecture and hands-on experience.

CEP304 Clinical Inve				
CEP304DOC	Revision	Н	Page 74 of 182	Medtronic

Trained product support personnel may be present at the training and study follow-up visits to provide technical support.

Trained personnel may also give technical support via the local support service, e.g. Medtronic 24HR Technical Support.

7.26 Product Receipt and Tracking

Upon receipt of the study devices, investigational center staff take inventory of the shipment, making sure that information on the packing slips/invoices matches exactly the contents of the containers, as applicable, including:

- Ship To
- Reference Number
- **Device Type**
- Quantity
- Quantity per package
- Lot number (where applicable)
- Serial number (where applicable)

Ensure that devices and supplies received have not reached their expiration date.

Sign and date the packing slips/invoices, noting any discrepancies, and file in appropriate study binder.

Notify the study Monitor of any discrepancies.

Enter the study device information on the appropriate eCRF in the study database.

7.27 Device Disbursement

Each time a study device is disbursed to a Subject by the Investigator or authorized member of the research team, all required eCRF and source documentation will be completed (see Table 8 for details). Documentation may include:

CEP304 Clinical In				
CEP304DOC	Revision	Н	Page 75 of 182	Medtronic

- Date of disbursement
- Subject ID
- Lot number(s)
- Serial Number
- Reference Number
- Amount dispensed

7.28 Product Storage

Study devices are to be stored in a secure environment with access limited to authorized research personnel. Study devices are to be stored in the proper environmental conditions, as identified in the user guide/labeling

7.29 Product Return

After use by the subject, the investigational center is expected to accept and retain all devices as described in Table 9 and store them in a secure environment. If containers/units/devices are missing, document the reasons in the eCRF. If discrepancies between amounts used by subjects and amounts expected to be returned exist, document the reasons in the eCRF.

All devices, as described in Table 9, will be returned by subjects to the investigational center and then to the Sponsor. Serialized devices provided to the investigational center may be returned as subjects complete the study, at the end of study or upon sponsor request. The quantity received by the investigational center and the quantity returned to sponsor should be equal. The investigational center will provide details of the disposition of all unreturned serialized devices (excluding the Study Meter and Ketone Meter) in the eCRF.

Used glucose sensors are not expected to be returned by subjects to the investigational center and therefore are not expected to be returned to the sponsor. Other unused consumable devices (i.e., infusion sets, alcohol wipes, Study Meter supplies, tape, etc.), supplies or materials may be returned to the sponsor or retained by investigational center for educational purposes only, or may be disposed of properly by the investigational center staff.

Disposable devices and supplies that have been *used* by a subject will be disposed of properly by the subject or the investigational center staff during the conduct of the study. This would include glucose sensors, meter

CEP304 Clinical I				
CEP304DOC	Revision	Н	Page 76 of 182	Medtronic

testing strips and supplies, infusion sets and adhesive tape.

All study devices that were required to be entered into the study database are required to be accounted for as described herein prior to return to sponsor or at the end of the study.

7.30 Product Accountability

Good clinical research practice requires that investigators and research teams ensure accurate accountability for any investigational device used in a research trial. It is expected that all investigational devices will be used in

the manner intended during the study, that they will be stored under appropriately controlled conditions with controlled access and that they will be used only by (on) subjects who have consented to participate in the research study.

Any investigational device being used in clinical research must be strictly accounted for and will not be shipped to any site unless all of the necessary approvals (e.g. Regulatory, IRB/EC) have been received. This includes keeping records of:

- 1. Center receipt and inventory management
- 2. Storage
- 3. Subject Disbursement
- 4. Return (by Subjects and Center) and/or disposal

During the conduct of the study the investigational center staff will account for, and document, the following:

Table 9. Device Accountability Requirements (U.S. Sites)

Device	Site Receipt (packing slip and eCRF)	Disbursement to Subject (eCRF)	Device Disposition at Conclusion of Study	Record Device Disposition (eCRF)
MiniMed 670G Insulin Pump (MMT-1780)	Yes	Yes	Return to Sponsor	Yes
MiniMed 770G Insulin Pump	Yes	Yes	Return to Sponsor	Yes

CEP304DOC Revision Н Page 77 of 182 Medtronic

Device	Site Receipt (packing slip and eCRF)	Disbursement to Subject (eCRF)	Device Disposition at Conclusion of Study	Record Device Disposition (eCRF)
(MMT-1880)				
CONTOUR® NEXT LINK 2.4 by Ascencia Blood Glucose Meter(MMT-1152 or MMT- 1352)	Yes	Yes	Dispose or return unused to Sponsor	Yes
Accu-Chek Guide Link Meter Blood Glucose Monitoring System (08116083022)	Yes	Yes	Return to Sponsor	Yes
Guardian Sensor (3) (MMT- 7020) – for 670G only	Yes	Yes	Dispose or return unused to Sponsor	Yes
Guardian Sensor (3) (MMT- 7020) – for 770G only	Yes	No	Dispose or return unused to Sponsor	No
One-Press Serter (MMT-7512)	No	No	Dispose or return unused to Sponsor	No
Guardian Link (3) Transmitter (MMT-7811) for 670G only	Yes	Yes	Return to Sponsor	Yes
Guardian Link (3) Transmitter (MMT-7910) for 770G only	Yes	Yes	Return to Sponsor	Yes
Tester (MMT-7736L)	No	No	Dispose or return unused to Sponsor	No
Transmitter Charger (MMT-7715)	No	No	Dispose or return unused to Sponsor	No
CareLink USB 2.4 GHz (MMT-7306)	No	No	Dispose or return unused to Sponsor	No
Ketone Meter	No	No	Dispose or return unused to Sponsor	No

CEP304 Clinical				
CEP304DOC	Revision	Н	Page 78 of 182	Medtronic

Devices may be combined and distributed in kits.

Table 10. Device Accountability Requirements (European Sites)

Device	Site Receipt (packing slip and eCRF)	Disbursement to Subject (eCRF)	Device Disposition at Conclusion of Study	Record Device Disposition (eCRF)
MiniMed 670G Insulin Pump (Europe MMT-1781, and MMT-1782)	Yes	Yes	Return to Sponsor	Yes
CONTOUR® NEXT LINK 2.4 by Ascencia Blood Glucose Meter (MMT-1352, Europe: MMT- 1151, MMT-1152)	Yes	Yes	Dispose or return unused to Sponsor	Yes
Guardian Sensor (3) (MMT-7020)	No	No	Dispose or return unused to Sponsor	No
Guardian Link (3) Transmitter (MMT-7811)	Yes	Yes	Return to Sponsor	Yes
Tester (MMT-7736L)	No	No	Dispose or return unused to Sponsor	No
One-Press Serter (MMT-7512)	No	No	Dispose or return unused to Sponsor	No
Transmitter Charger (MMT-7715)	No	No	Dispose or return unused to Sponsor	No
CareLink USB 2.4 GHz (MMT-7306)	No	No	Dispose or return unused to Sponsor	No
Ketone Meter	No	No	Dispose	No

Devices may be combined and distributed in kits.

CEP304 Clinical Investigation Plan CEP304DOC Revision Н Page 79 of 182 Medtronic

Table 11. Device Accountability Requirements (Canadian Sites)

Device	Site Receipt (packing slip and eCRF)	Disbursement to Subject (eCRF)	Device Disposition at Conclusion of Study	Record Device Disposition (eCRF)
MiniMed 670G Insulin Pump (Canada MMT-1781 (pump))	Yes	Yes	Return to Sponsor	Yes
MiniMed 770G Insulin Pump (Canada MMT-1881)	Yes	Yes	Return to Sponsor	Yes
CONTOUR® NEXT LINK 2.4 by Ascencia Blood Glucose Meter (Canada MMT-1351 or MMT- 1352)	Yes	Yes	Dispose or return unused to Sponsor	Yes
Accu-Chek Guide Link Meter Blood Glucose Monitoring System (08109222001)	Yes	Yes	Return to Sponsor	Yes
Guardian Sensor (3) (MMT- 7020) – for 670G only	Yes	Yes	Dispose or return unused to Sponsor	Yes
Guardian Sensor (3) (MMT- 7020) – for 770G only	Yes	No	Dispose or return unused to Sponsor	No
Guardian Link (3) Transmitter (MMT-7811WW), 670G only.	Yes	Yes	Return to Sponsor	Yes
Guardian Link (3) Transmitter (MMT-7911) 770G only	Yes	Yes	Return to Sponsor	Yes
Tester (MMT-7736L)	No	No	Dispose or return unused to Sponsor	No
One-Press Serter (MMT-7512)	No	No	Dispose or return unused to Sponsor	No
Transmitter Charger (MMT-7715)	No	No	Dispose or return unused to Sponsor	No

CEP304 Clinical Investigation Plan CEP304DOC Revision Page 80 of 182 Medtronic Н

Device	Site Receipt (packing slip and eCRF)	Disbursement to Subject (eCRF)	Device Disposition at Conclusion of Study	Record Device Disposition (eCRF)
CareLink USB 2.4 GHz (MMT-7306)	No	No	Dispose or return unused to Sponsor	No
Ketone Meter	No	No	Dispose	No

Devices may be combined and distributed in kits.

Table 12. Device Accountability Requirements (Australian Sites)

Device	Site Receipt (packing slip and eCRF)	Disbursement to Subject (eCRF)	Device Disposition at Conclusion of Study	Record Device Disposition (eCRF)
MiniMed 770G Insulin Pump (MMT-1881, MMT-1891)	Yes	Yes	Return to Sponsor	Yes
Accu-Chek Guide Link Meter Blood Glucose Monitoring System (08116113186M)	Yes	Yes	Return to Sponsor	Yes
Guardian Sensor (3) (MMT-7020C5) – for 770G only	Yes	No	Dispose or return unused to Sponsor	No
Guardian Link (3) Transmitter (MMT-7910WS, MMT-7911W) 770G only	Yes	Yes	Return to Sponsor	Yes
Tester (MMT-7736L)	No	No	Dispose or return unused to Sponsor	No
One-Press Serter (MMT-7512)	No	No	Dispose or return unused to Sponsor	No

CEP304 Clinical Investigation Plan CEP304DOC Revision Page 81 of 182 Medtronic Н

Device	Site Receipt (packing slip and eCRF)	Disbursement to Subject (eCRF)	Device Disposition at Conclusion of Study	Record Device Disposition (eCRF)
Transmitter Charger (MMT-7715)	No	No	Dispose or return unused to Sponsor	No
CareLink USB 2.4 GHz (Austalia, New Zealand)	No	No	Dispose or return unused to Sponsor	No
Ketone Meter	No	No	Dispose	No

Devices may be combined and distributed in kits.

Table 13. Device Accountability Requirements (New Zealand Sites)

Device	Site Receipt (packing slip and eCRF)	Disbursement to Subject (eCRF)	Device Disposition at Conclusion of Study	Record Device Disposition (eCRF)
MiniMed 770G Insulin Pump (MMT-1881, MMT-1891)	Yes	Yes	Return to Sponsor	Yes
Accu-Chek Guide Link Meter Blood Glucose Monitoring System (08116113186M)	Yes	Yes	Return to Sponsor	Yes
Guardian Sensor (3) (MMT-7020C5) – for 770G only	Yes	No	Dispose or return unused to Sponsor	No
Guardian Link (3) Transmitter (MMT-7910WS, MMT-7911W) 770G only	Yes	Yes	Return to Sponsor	Yes
Tester (MMT-7736L)	No	No	Dispose or return unused to Sponsor	No

CEP304 Clinical				
CEP304DOC	Revision	Н	Page 82 of 182	Medtronic

Device	Site Receipt (packing slip and eCRF)	Disbursement to Subject (eCRF)	Device Disposition at Conclusion of Study	Record Device Disposition (eCRF)
One-Press Serter (MMT-7512)	No	No	Dispose or return unused to Sponsor	No
Transmitter Charger (MMT-7715)	No	No	Dispose or return unused to Sponsor	No
CareLink USB 2.4 GHz (ACC-1003911D)	No	No	Dispose or return unused to Sponsor	No
Ketone Meter	No	No	Dispose	No

Devices may be combined and distributed in kits.

8. Selection of Subjects

Study Population 8.1

A diverse population of patients with type 1 diabetes will be studied. The study population will have a large range for duration of diabetes and glycemic control, as measured by glycosylated hemoglobin (A1C).

Subject Enrollment 8.2

Subjects will be considered enrolled in the study upon signing the Informed Consent/Assent form(s).

Inclusion Criteria 8.3

Subjects will be considered for enrollment in the study if they meet all of the following criteria:

1. Subject is age 2-80 years at time of screening

CEP304 Clinical I				
CEP304DOC	Revision	Н	Page 83 of 182	Medtronic

- a. US, Canada, Australia and New Zealand: Subjects 2-80 years of age will be allowed to enroll in the post approval study.
- b. Europe: Only subjects ≥7 years of age are allowed to enroll in the post-market study.
- 2. Subjects who are 2-21 years are determined by the investigator to have the appropriate, requisite support (family, caregiver or social network) to successfully participate in this study
- 3. Subject must have a minimum daily insulin requirement (Total Daily Dose) of equal to or greater than 8 units/day
- 4. Subjects who are determined by the investigator to be psychologically sound in order to successfully participate in this study.
- 5. Subject has been diagnosed with type 1 diabetes for at least three months

Note: Determination of classification for diabetes will be based on American Diabetes Association Clinical Practice Guidelines accounting for several patient characteristics such as: age of onset, patient's weight or BMI, history of diabetic ketoacidosis, history of therapy management, if available in the medical records.

- 6. Subject must be on one of the following management therapies:
 - Multiple daily injections defined by use of rapid analogue with meals and approved long acting analogue (e.g. detemir or glargine) with or without CGM
 - Insulin pump therapy with or without CGM
- 7. Subject is willing to perform ≥ 4 finger stick blood glucose measurements daily
- 8. Subject is willing to perform required study procedures
- 9. Subject is willing to wear the system continuously throughout the study for at least 80% of the time
- 10. Subject is willing to upload data at least weekly from the study pump/meter, must have Internet access and a computer system that meets the requirements for uploading the study pump/meter for data collection
- 11. Subject must be willing to use the study glucose meter system (i.e. along with study meter strips).
- 12. If subject has celiac disease, it has been adequately treated as determined by the investigator
- 13. Subject with the diagnosis of myocardial infarction, unstable angina, coronary artery bypass surgery, coronary artery stenting, transient ischemic attack, cerebrovascular accident, angina, congestive heart failure, ventricular rhythm disturbances or thromboembolic disease, within 1 year of screening, will be included in the study with the consent of the Investigator

CEP304 Clinical Inv				
CEP304DOC	Revision	Н	Page 84 of 182	Medtronic

- 14. Subject is willing to take one of the following insulins and can financially afford to use either of the 2 insulin preparations throughout the course of the study (i.e. co-payments for insulin with insurance or able to pay full amount)
 - a. Humalog® (insulin lispro injection)
 - b. NovoLog® (insulin aspart)

8.4 Exclusion Criteria

- 1. Subject participated in any Closed Loop study in the past
- 2. Subject is unable to tolerate tape adhesive in the area of sensor placement
- 3. Subject has any unresolved adverse skin condition in the area of sensor placement (e.g., psoriasis, rash, *Staphylococcus* infection) or area of infusion set placement
- 4. Women of child-bearing potential who have a positive pregnancy test at screening or plan to become pregnant during the course of the study
- 5. Subject is being treated for hyperthyroidism at time of screening
- 6. Subject has an abnormality (out of reference range) in thyroid-stimulating hormone (TSH) at time of screening visit. TSH is not required for subjects 2-13 years of age.
- 7. Subject has taken any oral, injectable, or IV glucocorticoids within 8 weeks from time of screening visit, or plans to take any oral, injectable, or IV glucocorticoids during the course of the study.
- 8. Subject is actively participating in an investigational study (drug or device) wherein he/she has received treatment from an investigational study drug or investigational study device in the last 2 weeks
- 9. Subject is currently abusing illicit drugs or marijuana
- 10. Subject is currently abusing prescription drugs
- 11. Subject is currently abusing alcohol
- 12. Subject is using pramlintide (Symlin), SGLT2 inhibitors, GLP agonists, biguanides, DPP-4 inhibitors or sulfonylureas at time of screening
- 13. Subject is using hydroxyurea at the time of screening or plans to use it during the study
- 14. Subject has a history of visual impairment which would not allow subject to participate in the study and perform all study procedures safely, as determined by the investigator

CEP304 Clinical 1				
CEP304DOC	Revision	Н	Page 85 of 182	Medtronic

- 15. Subject has a sickle cell disease, hemoglobinopathy; or has received red blood cell transfusion or erythropoietin within 3 months prior to time of screening
- 16. Subject plans to receive red blood cell transfusion or erythropoietin over the course of study participation
- 17. Subject diagnosed with current moderate to severe eating disorder such as anorexia or bulimia
- 18. Subject has been diagnosed with chronic kidney disease requiring dialysis or resulting in chronic anemia
- 19. Subjects who are currently being actively treated for cancer.
- 20. Subject who is designated as a research staff member for this study

9. Study Site Requirements

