For example: If a sensor falls out on Day 4, a replacement sensor should be inserted. Once that replacement sensor has been worn for 7 days, a new sensor should then be inserted and worn for 3 days so that a total of 14 days of sensor wear is completed.

All patients will wear blinded CGM. Subjects will be expected to demonstrate sensor wear for approximately 14 days total between the two 7-day sensor wears (plus replacement sensor if needed). Subjects should be instructed to make 4-6 BG measurements per day.

CEP304 Clinical				
CEP304DOC	Revision	Н	Page 54 of 182	Medtronic

3. Continuation Period: There will be a 6 month continuation period during which time all subjects will use the HCL system.

Enrollment Cohorts According to Treatment

At Enrollment, subjects will be identified according to the type of treatment regimen they are currently on. Treatment regimen is defined as follows:

- Cohort 1: CSII subjects using pump (Medtronic or other pump systems) for at least 3 months at time of screening without concurrent use of real time CGM in the last 3 months. (Self-report acceptable.) Please note that alternatives to SMBG such as Freestyle Libre are not considered real time CGM and subjects who are using Freestyle Libre at time of Screening will be allowed to enroll in the study. During the study, however, subjects will not be allowed to use Freestyle Libre.
- Cohort 2: Multiple Daily Injections (MDI) Subjects using MDI with or without concurrent use of CGM for at least 3 months prior to Screening. (Self report is acceptable.)
- Cohort 3: Sensor Augmented Pump (SAP) subjects using pump for at least 3 months at time of screening with real time CGM use (Medtronic or other CGM systems) approximately 20% of the time. (Self report acceptable.) Subjects will use the Medtronic CGM starting at Visit 3, but they may use their own CGM until then. Sensor insertion placement will be according to User guide.

Staged enrollment for Subjects 2-6 Years of Age:

Subjects 2-6 years of age will be allowed to enroll in the post approval study, once DMC has reviewed data from 10 subjects age 2-4 years who have completed participation in the study period of the CEP302 study and has given approval to enroll

In the US and Canada, subjects 2-80 years of age will be allowed to transition from the 670G system to the 770G system.

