 - a) The Sensor Augmented Pump (SAP) subjects will use the MiniMed System (SAP without Low Management Suspend on Low, Low Management Suspend before low or Auto Mode) with Real Time CGM for the 6 month study period. There will be N=140.

The Continuation Period: All subjects above will enter the continuation period for 6 months using the MiniMed system with Auto Mode on.

Figure 2. Study Design

Subjects may be re-tested as per sponsor discretion.

CEP304 Clinical Investigation Plan CEP304DOC Revision Н Page 57 of 182 Medtronic

Per Cohort (CSII, MDI, or SAP), here is the numbers of subjects expected to enroll:

- A1C at time of screening:
 - \circ N = 70 A1C > 8% for HCL Arm
 - $N = 70 \text{ A1C} \le 8\% \text{ for HCL Arm}$
 - O N = 70 A1C > 8% for Control Arm
 - N = 70 A1C \leq 8% for Control Arm
- Age at time of screening:

N=Minimum number of eligible subjects for each age group within each treatment cohort		N= Minimum number of eligible Subjects for each age group and cohort	N=Minimum number of eligible subjects for each age group for study		
Age Group	Cohort	N	N	N	
	CSII				
2-6 years	SAP	No Minimum	No minimum	N= 120	
	MDI				
	CSII		No minimum	N= 180	
7 -13 years	SAP	No Minimum			
	MDI				
	CSII		N=45	N=135	
14-21 years	SAP	N= 45			
	MDI				
	CSII				
22-64 years	SAP	N= 120	N=120	N=360	
	MDI				
	CSII				
65-80 years	SAP	No Minimum	No minimum	N=150	
	MDI				

CEP304 Clinical Investigation Plan CEP304DOC Medtronic Revision Н Page 58 of 182

Table 3. Randomization

Treatment at Baseline	Randomization Options	Continuation	
CCII	CSII	uci	
CSII	HCL	HCL	
MDI -	MDI	IICI	
	HCL	HCL	
SAP -	SAP		
	HCL	HCL	

Note: Subjects 2-6 years of age will automatically enter the HCL arm at the end of the run-in period

Table 4. Site Enrollment (approximate schedule from Protocol approval)

Month Enrollment Timelines	Actual Site Enrollment (per month)	Site Enrollment Timelines
Month 1-48	April 2017 to March 2021	37
Month 49-52	April 2021 to July 2021	45

Table 5. Subject Enrollment at 2-3 month intervals (approximate schedule from first enrollment)

Month Enrollment Timelines	Actual Month Intervals	Subject Enrollment Timelines
Month 1-43	May 2017 to December 2020	930
Month 44 -50	January 2021 to June 2021	1080

CEP304 Clinical 1				
CEP304DOC	Revision	Н	Page 59 of 182	Medtronic

Month Enrollment Timelines	Actual Month Intervals	Subject Enrollment Timelines
Month 51-56	July 2021 to December 2021	1120*

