7.2 Intended Population

A diverse population of patients with type 1 diabetes will be studied. The study population will have a large range for duration of diabetes and glycemic control, as measured by glycosylated hemoglobin (A1C). They will be enrolled in the study regardless of their prior diabetes regimen, including using Multiple Daily Injections (MDI), Continuous Subcutaneous Insulin Infusion (CSII) or Sensor-Augmented Pump therapy (SAP).

CEP304 Clinical				
CEP304DOC	Revision	Н	Page 61 of 182	Medtronic

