7.4 MiniMed 670G Insulin Pump

The MiniMed 670G Insulin Pump is capable of continuous insulin delivery, at set and variable rates, for the management of diabetes mellitus in persons requiring insulin. When used with the CGM components (Guardian Sensor (3), Guardian Link (3) Transmitter), the pump system is capable of continuous or periodic monitoring of glucose levels in the interstitial fluid under the skin and detection of possible low or high blood glucose episodes. The pump also displays continuous glucose values, storing this data so that it can be retrospectively analyzed to track patterns and improve diabetes management. These features are similar to the commercially available Medtronic sensor-enabled system (e.g. MiniMed 530G System (P120010) in the US, MiniMed 640G and Veo System OUS, which has the threshold suspend feature).

The MiniMed 670G Insulin Pump also includes the closed loop algorithm as part of the SmartGuard™ collection of features that may be enabled by the user. SmartGuard is comprised of Manual Mode Low Management, which includes the suspend on low feature (suspends insulin delivery when a pre-set low SG threshold is reached), the suspend before low feature (enables insulin to suspend 30 minutes before a pre-set low SG threshold is reached) and Auto Mode (hybrid closed loop) feature. The Auto Mode and Manual Mode -Low Management features will not be active at the same time.

The pump may also be used as a simple pump without CGM or as a sensor augmented pump without the SmartGuard features.

When Auto Mode is enabled on the MiniMed 670G insulin pump, the sensor glucose (SG) values received from the Guardian Link (3) Transmitter by the insulin pump will be used to automatically calculate the insulin dose. It will then deliver insulin to the patient, at five minute intervals, to achieve glycemic control.

With the HCL system, subjects must still deliver bolus insulin for meals as calculated by the insulin to carbohydrate ratio. This ratio is determined by the Health Care Professional (HCP)/patient. In addition, the

^{**} Determined to be a Medical Device Data System by the Medical Device Directorate and as such not subject to the Canadian Medical Device Regulations.

CEP304 Clinical 1				
CEP304DOC	Revision	Н	Page 66 of 182	Medtronic

setting for active insulin must be programmed. Basal rates are set for period of open loop therapy.

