10.1 Overview

Run-In Period Synopsis (Run-in Visits 1-3)

The purpose of the run-in period is to ensure that study subjects are introduced to study devices and to provide blinded CGM data. Subjects will be trained on CGM use and blinded CGM will be used to collect

CEP304 Clinical				
CEP304DOC	Revision	Н	Page 86 of 182	Medtronic

data with each subject's existing diabetes therapy. There is a window of 60 days from the end of Visit 1 to the end of Visit 3 during which time subjects should complete run-in. Subjects will be started on the study pump at Visit 3.

Devices Worn:

- Medtronic CGM (blinded) only
- Depending on age group, sensor is self-inserted by subject or inserted with assistance
- Existing Therapy

Study Period Synopsis

Overview:

The study period is 6 months Subjects will be randomized at the start the study period into 2 arms:

- HCL Arm: Auto Mode feature on the study pump turned ON
- Control Arm: Continue with own therapy for 6 months
 - CSII Cohort: The CSII Cohort will use the MiniMed Pump without Real Time CGM during the 6 month study period. Blinded CGM (Guardian Link (3) Transmitter and Guardian Sensor (3)) will only be worn at baseline, 3 months, and 6 months (two weeks of sensors use)
 - MDI Cohort: The Multiple Daily Injection (MDI) Cohort will remain on MDI therapy with subjects using their own insulin for 6 months during the study period. Blinded CGM (Guardian Link (3) transmitter and Guardian Sensor (3)) will only be worn at baseline, 3 months, and 6 months (two weeks of sensors use).

MDI subjects who are currently using CGM, i.e. Dexcom or Medtronic Guardian Connect

CEP304 Clinical In				
CEP304DOC	Revision	Н	Page 87 of 182	Medtronic

- or who are currently using a SMBG alternative, i.e. Libre, will be allowed to enroll in the study and continue using their own device. There will be N=100
- SAP Cohort: The Sensor Augmented Pump (SAP) Cohort will use the MiniMed Pump (SAP without Low Management Suspend on Low, Low Management Suspend before low or Auto Mode) with Real Time CGM for the 6 month study period

Note: Subjects 2-6 years of age will automatically enter the HCL arm at the end of the run-in period

Study Period Device Procedures for HCL Arm

Devices Worn:

- MiniMed Pump
- Depending on randomization and age group, sensor is self-inserted by subject or inserted with assistance

Calibration Requirements with Study Meter:

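### Cohort 3 can enrol current users of marketed Auto Mode or low-suspend systems, so for them the randomized contrast measures withdrawal of automation, not its addition to SAP therapy

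*Protocol*

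**What the plan says.** **Eligibility.** Protocol 8.4, exclusion 1, reads "Subject participated in any Closed Loop study in the past". The only other exclusion touching on devices under study is no. 8, which begins "Subject is actively participating in an investigational study (drug or device) wherein he/she has received treatment" and covers the last 2 weeks. Inclusion 6 (Protocol 8.3) accepts "Insulin pump therapy with or without CGM", and Protocol 7.2 says of the population: "They will be enrolled in the study regardless of their prior diabetes regimen". None of the 14 inclusion or 20 exclusion criteria mentions use of a commercial closed-loop or low-suspend system.

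**Cohort 3 entry** (Protocol Section 6; repeated in SAP Section 5). Pump use for at least 3 months, "with real time CGM use (Medtronic or other CGM systems) approximately 20% of the time", self-report accepted. Cohort 1, by contrast, carries an explicit look-back rule: no real-time CGM in the last 3 months.

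**Market status.** Protocol Table 7 lists the 670G pump, with its closed-loop algorithm, as non-investigational in the US (ages 7-80), licensed in Canada and CE marked in Europe (both from age 7). Protocol 7.4 also names marketed low-suspend systems, including "MiniMed 640G and Veo System OUS, which has the threshold suspend feature". Table 6 counts from protocol approval or device launch and places the last enrolment at 55-57 months.

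**Baseline and control.** Run-in CGM is collected on the subject's own therapy, and own CGM may be used until Visit 3 (Section 6). Baseline A1C is taken at the randomization visit (5.2.1). The Cohort 3 Control arm then uses "SAP without Low Management Suspend on Low, Low Management Suspend before low or Auto Mode" for 6 months. The Study Period Synopsis in 10.1 introduces the control as "Control Arm: Continue with own therapy for 6 months", and 10.6 describes it in similar terms.

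**The concern.** Cohort 3 is meant to show what HCL adds to sensor-augmented pump therapy. For a person already on commercial Auto Mode, assignment to HCL changes little, and assignment to Control takes the test therapy away. For a low-suspend user, assignment to Control removes a feature that the HCL arm may still use when Auto Mode is off (10.1, Manual Mode Settings).

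The Cohort 3 estimate then mixes two questions: the effect of starting HCL from SAP, and the effect of stopping automation. Within-arm changes become hard to read, because part of the HCL arm is already treated at baseline and part of any Control deterioration comes from withdrawal. If some benefit persists after withdrawal, the contrast shrinks and power falls. Both co-primaries must succeed for a cohort claim (19.1.6), so a loss in either A1C group matters.

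**Working it through.** **Step 1. Can such a person enter, and in which cohort?** Cohort 1 excludes recent real-time CGM, so sensor-driven automation is ruled out there. Cohort 2 is on injections. Subjects aged 2-6 go straight to HCL and are not randomized. Only randomized Cohort 3 subjects are exposed. A 670G Auto Mode user is a pump user with real-time CGM, meets inclusion 6 and the Cohort 3 definition, and meets no exclusion unless previously in a closed-loop study.

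**Step 2. What therapy does baseline reflect?** Run-in is on own therapy with own CGM allowed, and A1C is drawn at the end of run-in. Both baselines therefore reflect the automated therapy. Time below 70 mg/dL is analysed as a level during the study period, not as a change, so there the issue lies in what Control subjects have given up.

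**Step 3. Effect on the contrast.** The plan shows no effect size or power in the visible text (the sample-size section is not visible), so there is no plan figure to reproduce beyond the counts: 70 + 70 = 140 per arm and 140 + 140 = 280 per cohort in the Protocol.

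Assumptions: a share f of each 70-subject cell are prior Auto Mode users; HCL effect δ is the same in all; prior users assigned to HCL do not change; a fraction r of the benefit is lost in prior users assigned to Control.

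- HCL-arm mean change: (1 − f)δ
- Control-arm worsening: f·r·δ
- Contrast: δ[1 − f(1 − r)]

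With r = 1 (full reversal) the contrast is δ whatever f is. For an assumed A1C effect of −0.5 and f = 10% or 30%, HCL change is −0.45 or −0.35 and Control change +0.05 or +0.15; the difference is −0.50 both times. The contrast is intact, but 10% to 30% of it is deterioration in Control.

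With r = 0 (no reversal) the contrast is (1 − f)δ. Take δ as the difference that 70 per arm detects at one-sided 0.025, in SD units: δ = (1.960 + z_power) × √(2/70), which is 0.474 at 80% power and 0.548 at 90%. Power under dilution is Φ[(1 − f)(1.960 + z_power) − 1.960], and the number per arm that restores it is about 70/(1 − f)².

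| f | Power, from 80% | Power, from 90% | N per arm to restore |
|---|---|---|---|
| 10% | 71% | 83% | 87 |
| 20% | 61% | 74% | 110 |
| 30% | 50% | 62% | 143 |

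Check for f = 20%, from 80%: 0.8 × 2.802 − 1.960 = 0.281, and Φ(0.281) = 0.61. Partial reversal lies between the extremes: f = 20% with r = 0.5 gives a contrast of 0.9δ, the same as the first row.

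**The case against.** Much of the case on the other side stands.

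*Validity.* Randomization is within cohort and A1C group, so prior users fall in both arms by chance and type I error is unaffected. A reader might infer that HCL superiority becomes easier to show, above all for time below 70 mg/dL in Group 2. The documents do not support that. Outcomes are measured on the assigned therapies, and the comparator has automation off for everyone in it. Under the model above the effect is neutral or conservative.

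*Inflation.* A reader might argue that people who stay on commercial Auto Mode respond better, so the estimate is too large for SAP users. The sign rests entirely on the assumption. With full reversal, an effect of 0.5 in other subjects and 0.8 in prior users, the mixed effect is 0.9 × 0.5 + 0.1 × 0.8 = 0.53 at f = 10%, and 0.7 × 0.5 + 0.3 × 0.8 = 0.59 at 30%: 6% to 18% too large. With 0.2 in prior users it is 0.47 and 0.41: 6% to 18% too small. The weaker response is at least as natural in Group 1, where such a person has A1C above 8% while already on Auto Mode.

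*Contradiction.* The own-therapy line in 10.1 might be read as promising controls a protection that they then lose. It is a loose heading; the SAP sub-bullet beneath it says that the features are off. The wording needs aligning, but the comparator is openly defined.

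*Intent.* The randomization table lists only CSII, MDI and SAP as baseline treatments, which may imply that Auto Mode users were not meant to enter, and broad eligibility is deliberate in a post-approval study. Still, the operational definition is silent. The 10.10 rule on repeated SmartGuard use against instruction acts during the study and does not screen prior users.

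*Visibility.* The supportive-analysis section (Protocol 19.1.8), parts of the SAP and the visit tables are not visible. A baseline flag, a sensitivity analysis or a run-in instruction may exist there.

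**Conclusion.** The gap holds on the face of the eligibility text, which is visible in full. Cohort 3 admits current Auto Mode and low-suspend users, takes their baseline on that therapy, and may assign them to a control without it. This is a problem of what the estimate means, with a possible loss of power. It does not invalidate the comparison.

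The size is conditional. At assumed shares of 10% to 30%, the result ranges from no change in the contrast (full reversal) to a fall from an assumed 80% power to 71%-50% (no reversal). The documents give neither the share nor the degree of reversal, so the direction of any net bias is unknown, and they do not show that any such subject was enrolled. The power figures model prior Auto Mode users. Low-suspend users are not on the test therapy at baseline, so for them only the withdrawal in Control applies.

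**What to change.** 1. For remaining enrolment, add to the Cohort 3 definition: *without use of a hybrid closed loop (Auto Mode) system in the last 3 months*. This mirrors the Cohort 1 rule on real-time CGM and leaves the other cohorts alone. Against Table 5's target of 1120, with 959 already enrolled, at most 1120 − 959 = 161 enrolments across all cohorts remain, so this step alone does little.
2. For all Cohort 3 subjects, record Auto Mode and low-suspend use at baseline from the screening therapy record. Unless the sections not visible already do so, pre-specify a repeat of both co-primary analyses without the flagged subjects. This covers low-suspend users, whom step 1 leaves eligible.
3. Reconcile the own-therapy wording in 10.1 and 10.6 with the Cohort 3 control, so that the claim reads HCL versus SAP with suspend features and Auto Mode off.

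Cost: one line in the cohort definition, one baseline variable, one sensitivity analysis and a wording change. The downside is a slightly smaller pool for the remaining Cohort 3 recruitment and a more narrowly worded claim.
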